## 1. Objectives

- 1.1. The objective of this research is to perform a non-masked, non-inferiority randomized controlled trial to assess the quality of life (QOL) of women with idiopathic overactive bladder (OAB) before and after treatment with percutaneous tibial nerve stimulation (PTNS) or transcutaneous electrical nerve stimulation (TENS) of tibial nerve. The target population is patients with OAB who previously failed first- and second-line treatments and desire non-surgical management.
- 1.2. Our central hypothesis is that a TENS unit is non-inferior to PTNS for improving the quality of life and symptom distress of women with OAB. The specific aims are:
  - 1.2.1. To compare the effects on health-related quality of life (HRQoL) and symptom bother as measured by the change in score from baseline of the Overactive Bladder questionnaire (OAB-q) in women with urgency urinary incontinence or overactive bladder before and after PTNS versus TENS after 3 months of therapy. Secondary outcomes related to this aim include change in symptom bother alone, as measured by the OAB-q symptom subscale and change in HRQL alone, as measured by the OAB-q HRQL subscale from baseline. **Hypothesis:** TENS will demonstrate similar effects on symptoms and symptom-associated HRQoL in the treatment of women with OAB compared to PTNS.
  - 1.2.2. To compare the rates of treatment success, as defined as 50% or more reduction of urinary incontinence episodes or 25% or more reduction in day or night voids in women with OAB before and after PTNS versus TENS after 3 months of therapy. The number of urinary incontinence episodes, number of voids per day and number of voids per night will be measured by a three-day voiding diary. **Hypothesis:** TENS will demonstrate similar rates of treatment success in women with OAB compared to PTNS.
  - 1.2.3. To perform a comparative analysis of patient satisfaction and compliance between TENS and PTNS. Patient satisfaction will be measured by a patient satisfaction question (PSQ). Patient compliance will be measured by number of treatment sessions completed as verified by clinical records of completed PTNS treatments and TENS device interrogation. **Hypothesis:** Women will be satisfied with both TENS and PTNS treatment and will have greater treatment compliance with TENS compared to PTNS.

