RCTs and 3 prospective cohorts. Women also view TENS as a convenient, beneficial and acceptable treatment of OAB. A qualitative study by Daly et al. revealed TENS home treatment allowed for flexibility to accommodate lifestyle and work needs, unlike clinic visits, and provided a sense of control and empowerment over their OAB symptoms that facilitated their willingness and motivation to continue treatment and improve self esteem^26. The home was viewed as a safe space for women to receive treatment without the stress and embarrassment of clinic visits for their condition. Women in the study often viewed TENS as both a mental and physical treatment. The at home self-administration makes TENS treatment a viable way to reduce obstacles patients face accessing care. This is encouraging evidence that TENS may provide a safe, effective, convenient and possibly preferred alternative treatment to PTNS for OAB.

To date, there are very limited studies directly comparing PTNS and TENS for the treatment of OAB. Ramírez-García et al. compared PTNS to transcutaneous stimulation of the posterior tibial nerve for the treatment of OAB and demonstrated transcutaneous tibial nerve stimulation was non-inferior in decreasing daytime frequency, urinary incontinence episodes and quality of life. However, both interventions in this study were performed in a clinical setting and once a week, overlooking the two significant advantages TENS provides over traditional PTNS: self-administered treatment at home and increased frequency of treatment. Another RCT comparing PTNS to TENS, in which the TENS group received daily treatments at home, did not demonstrate a difference between groups in reductions of incontinence episodes, number of voids or quality of life measures (unpublished data). However, this study was underpowered to determine equivalency or non-inferiority. The authors are unaware of any other trials directly comparing TENS and PTNS treatment for OAB. Given this gap in knowledge and the advantages TENS can offer to reduce barriers to accessing healthcare, we propose to study home TENS versus traditional, office-delivered PTNS for women with OAB. This innovative research shows promise in helping patients overcome a costly and embarrassing condition in the privacy of their own homes, on their own time.

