### **3. Study Design**

We plan to perform an unmasked, non-inferiority randomized controlled trial to determine if the quality of life is improved with the use of TENS compared to PTNS for urgency urinary incontinence and overactive bladder. The target population is patients with OAB and/or urgency urinary incontinence (UUI) who present to the urogynecology clinic either at the University of New Mexico Hospital (UNMH) or Sandoval Regional Medical Center (SRMC). Women will be informed of the arm of the study to which they are randomized, as the intervention is unable to be masked. Masking is not possible with this study design due to the nature of the interventions. All women will give written consent prior to enrollment.

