## 5. Number of Subjects

5.1. This is a single-center study at the University of New Mexico, therefore the total number of subjects at the University of New Mexico is the total number of subjects for the study.

5.2. The total number of subjects to be recruited at this site is up to 130 patients.

5.3. *Sample size calculation:* The primary outcome for this study is the change in the OAB-q total score from baseline to 3 months. We used the means and standard deviation for this questionnaire from an unpublished pilot RCT study from Walter Reed that compares PTNS and TENS for the treatment of OAB (unpublished work). We have powered the study based on a 10-point difference as significant between groups. This 10-point difference used for the power calculation is based on the previously established minimum important difference. To achieve power for this non-inferiority RCT study showing that the difference between groups is less than 10 points, we need 40 patients per group (80 total) to detect no difference with  $\alpha = 0.05$  and 80% power. Allowing for dropout of up to 30%, we will aim to randomize 114 patients, and will plan to recruit up to 130 to allow for potentially higher drop-out, as the study primary outcome is at the 12 weeks' time point. As we plan to perform both per-protocol and intention-to-treat analysis, the sample size must be met for both per-protocol and intention-to-treat analysis, with the per-protocol patients (those in the PTNS group completing at 12 treatments in a total of 13 weeks) being expected to be a lower sample size.

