## 12. Procedures

This non-blinded, non-inferiority randomized controlled trial will be conducted at the UNM Eubank Clinic and SRMC Urogynecology clinic. Each site will recruit participants and we will plan to obtain up to 130 women between the two sites. Collaborating investigators will be members of the Urogynecology Division at UNM HSC.

The primary aim of our study is to determine if symptoms and quality of life related to overactive bladder are improved similarly with TENS use versus PTNS in women with OAB/UUI. The target population will be patients with OAB or UUI who are seeking care after failing first- and second-line therapies. According to the American Urologic Association, first line therapy includes conservative treatments like bladder training, bladder-control strategies, pelvic floor muscle training or fluid management. Second-line treatment includes pharmacologic management with anti-muscarinic and  $\beta$ 3-adrenoceptor agonist medications. Subjects must have failed a trial of at least one medication (use with no improvement in symptoms for at least 8 weeks, or a contraindication to taking medication such as narrow angle glaucoma, use of other medications that would interact with anticholinergics, uncontrolled hypertension, allergic reaction or adverse side effect to an anticholinergic medication). The subject may have stress urinary incontinence, but urinary urgency or urgency urinary incontinence must be a bothersome complaint or symptom. The current standard-of-care recommendation for those with refractory OAB or UUI who have failed first- and second-line therapies is to offer patients third-line treatment with PTNS, sacral neuromodulation, or intradetrusor injection of onabotulinumtoxinA. For patients who present for treatment of refractory OAB or UUI, we will take a thorough history and physical and counsel the patient on all of her options including medical and surgical interventions.

If the patient is interested in non-surgical management with PTNS and fulfills study inclusion criteria, we will then offer her the choice of volunteering for the study. All women will give written and/or electronic consent prior to their enrollment at this time and fill out baseline questionnaires in the clinic. Research staff and clinicians will obtain consent and administer study. After enrollment, participants will fill out a baseline OAB-q and will be

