### 13.Data Analysis

- 13.1. *Data Analysis:* Between and within group differences will be evaluated using Fisher's exact test for categorical variables and t-tests for continuous variables, as we expect the data will be normally distributed. Wilcoxon rank-sum test will be used for continuous variables that are not normally distributed. If there are any baseline differences between groups, a multivariate analysis will determine the contribution of these differences to observed differences (if any) between groups.
- 13.2. *Intention-to-treat analysis:* We plan to perform the primary analysis as "intention-to-treat" indicating that patients will be analyzed in the group to which they were randomized, regardless of compliance with study procedures, unless they asked to be withdrawn or were withdrawn by investigators due to safety or validity concerns. For example, PTNS patients that miss more than one session or do not make up a missed session of their office PTNS would still be analyzed in the "intention-to-treat" analysis as being in the PTNS group.
- 13.3. *Per protocol analysis:* We plan to perform a secondary analysis as "per protocol" indicating that patients will be analyzed in the group to which they were randomized only if they complete a full 12 weeks of treatment in compliance with study procedures, meaning that women assigned to the PTNS arm completed 12 weekly PTNS sessions in the office in 13 weeks or less, and women in the at-home TENS arm performed TENS stimulation at least 5 days per week for 12 weeks, as averaged over 12 weeks. For example, PTNS patients that miss more than one session or do not make up a missed session of their office PTNS will not be analyzed in the "per protocol" analysis as being in the PTNS group.
- 13.4. *Power Analysis:* Power analysis was performed based on previously reported means and standard deviation for the OAB-q. The primary outcome of this study is improvement in HRQL and symptom bother of OAB/UUI as measured by the OAB-q. We used the means and standard deviation for this questionnaire from a prior unpublished pilot RCT from Walter Reed comparing PTNS and TENS for the treatment of OAB. We have assumed a change score of greater than 10 points to be significant between groups based on the minimally important difference that has been previously established. To achieve significance for a non-inferiority study using these assumptions we would need 80 patients,

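### Section 13 names only tests of difference for a non-inferiority trial: the 10 points of Section 5.3 have no decision rule, and alpha has no sidedness

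*Combined protocol and SAP*

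**What the plan says.** The protocol presents itself as a non-inferiority trial throughout. Section 1.2 states: "Our central hypothesis is that a TENS unit is non-inferior to PTNS". Section 3 says "We plan to perform an unmasked, non-inferiority randomized controlled trial", and Section 12 repeats the label.

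Section 5.3 makes the change in OAB-q total score from baseline to 3 months the primary outcome. It sizes the trial for "showing that the difference between groups is less than 10 points", and says "we need 40 patients per group (80 total) to detect no difference with" alpha = 0.05 and 80% power. The 10 points come from a published minimum important difference. The SD comes from an unpublished pilot trial and is not printed. Neither 5.3 nor 13.4 says whether alpha is one-sided or two-sided.

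Section 13.1 covers between-group and within-group differences for all variables: Fisher's exact test for categorical data, "t-tests for continuous variables, as we expect the data will be normally distributed", a rank-sum test for non-normal continuous data, and a multivariate analysis if baselines differ. It does not mention the OAB-q, but no other method is given, so it governs the primary outcome by default. Section 13.2 makes intention-to-treat the primary analysis and 13.3 makes per-protocol secondary. Section 13.4 repeats the sizing, but there the 10 points are the between-group change that counts as significant, and 40 per group is the number needed to detect it. Section 5.3 adds that "the sample size must be met for both per-protocol and intention-to-treat analysis".

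Nowhere do the documents name a confidence interval or bound, a null hypothesis shifted by 10 points, a direction, or a rule for declaring non-inferiority.

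**The concern.** A test of difference has zero as its null. Non-inferiority has a 10-point deficit as its null. A non-significant test of difference does not exclude a 10-point deficit. A significant one, taken alone, does not show non-inferiority either: only a result significantly in favour of TENS would imply it, by way of superiority, which is not what the trial is sized to find. Followed as written, 13.1 does not test the central hypothesis.

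The two accounts of the sizing also pull apart. Section 5.3 describes excluding a difference of 10 points, while 13.4 describes detecting one.

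The trial is unmasked. With no rule fixed in advance, the same data could be judged by a test of difference, a 90% interval or a 95% interval after results are seen, and these can disagree.

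**Working it through.** **Inputs.** From 5.3 and 13.4: 10 points, 40 per group, 80% power, alpha 0.05. Allocation is 1:1 (Section 12). Assumed, because not stated: a true difference of 0, and sidedness taken both ways.

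**1. The plan's own figure.** Without an SD, 40 per group can be neither reproduced nor refuted. The SD it implies follows from n = 2·SD²·(z_α + z_β)² / 10², so SD = 10·√(40/2) / (z_α + 0.8416):

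- One-sided 0.05: 44.72 / (1.6449 + 0.8416) = 17.99, about 18.
- One-sided 0.025: 44.72 / (1.9600 + 0.8416) = 15.96, about 16.

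A two-sided 5% superiority test for a 10-point difference uses the same 1.9600 and also gives about 16. The number 40 therefore does not reveal which test was meant.

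**2. Where a test of difference and a margin rule disagree.** At 40 per group, SE = SD·√(2/40) with 78 df; t = 1.991 (95% interval) and 1.665 (90% interval).

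| SD | SE | 95% half-width | 90% half-width | Largest deficit passing, 95% | Largest deficit passing, 90% |
|---|---|---|---|---|---|
| 18 | 4.025 | 8.01 | 6.70 | 10 - 8.01 = 1.99 | 10 - 6.70 = 3.30 |
| 16 | 3.578 | 7.12 | 5.96 | 10 - 7.12 = 2.88 | 10 - 5.96 = 4.04 |

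A two-sided 5% t-test is non-significant for any deficit below the 95% half-width. Pairing each SD with the alpha that implies it:

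- SD 18, 90% interval: a deficit from 3.3 to 8.0 points is non-significant but fails the 10-point rule.
- SD 16, 95% interval: the same holds from 2.9 to 7.1 points.

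**3. What the missing sidedness is worth.** Power to show non-inferiority at a true difference of 0 and 40 per group (non-central t):

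- SD 18: 79% with a 90% interval, 69% with a 95% interval.
- SD 16: 79% with a 95% interval.

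The matched pairs fall just short of 80% because the back-solve used the normal formula.

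**4. A labelled hypothetical.** Suppose non-significance on a two-sided 5% t-test were read as similarity. With a true TENS deficit of 10 points and 40 per group, the chance of p > 0.05 is 21% at SD 16 and 31% at SD 18. A margin rule would hold this error at 2.5% or 5%.

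**5. Requiring both analysis sets to pass.** Take SD 18, a true difference of 0, 45 per arm for intention-to-treat (130 × 0.7 = 91, about 45 per arm) and an assumed random 40 of those 45 for per-protocol. By simulation, power goes from 83% (intention-to-treat alone) to 77% (both) with a 90% interval, and from 74% to about 67% with a 95% interval.

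**The case against.** **The margin is in the protocol.** This stands. Section 5.3 states the 10-point aim, so it would be wrong to say the trial has no margin. The fault is that 13.1 to 13.3 do not use it and 13.4 recasts it.

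**A t-test can be run against a 10-point null, and so can a rank-sum test.** Also true. A reader might infer that the rank-sum fallback cannot serve a margin at all. Under a location-shift model it can: simulated with normal data, SD 18, 40 per arm and one-sided 0.05, a rank-sum test shifted by 10 had about 5% type I error and 76 to 77% power. The defect is the same for both tests: 13.1 states no shift.

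**The investigators will not mistake non-significance for non-inferiority.** A reader might infer that they plan to, since the aims in 1.2 speak of similar effects. The documents do not say so, and Section 2 counts against it: of an earlier trial that found no difference between groups, it says "this study was underpowered to determine equivalency or non-inferiority". The 21 to 31% figure is therefore a hypothetical and not the plan's error rate.

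**Both sets must pass.** A reader might infer this from the demand for adequate size and power in both sets. That demand is not a decision rule. Section 13.2 makes intention-to-treat primary, and on the ordinary reading the primary analysis decides.

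None of this supplies the missing bound, direction or level.

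**Conclusion.** The point holds and must be fixed before outcome data are analysed. The method that governs the primary outcome is a test of difference, the 10-point aim has no place in the analysis, and the level is undefined.

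In size, under the back-solved SDs, there is a band of observed deficits about 4 to 5 points wide (8.0 - 3.3 = 4.7; 7.1 - 2.9 = 4.2) in which a test of difference finds nothing and a margin rule fails. At SD 18, the choice of interval level moves power by about 10 points (79% against 69%).

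These figures rest on SDs inferred from 40 per group and on an assumed true difference of 0. They illustrate the consequences of the gap and do not show that 40 per group is wrong. That the rule, direction and sidedness are missing depends on no assumption.

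**What to change.** - **Rule (13.1).** For the primary outcome, declare TENS non-inferior if the lower confidence bound for the TENS minus PTNS difference in mean change in OAB-q total score at 12 weeks, scored so that higher is better, lies above -10.
- **Score.** Say how the total score is formed and oriented. Section 12.2.1 describes only symptom-bother items, HRQL subscales and a total HRQL score.
- **Level.** Match it to the alpha used in sizing: a 90% interval for one-sided 0.05, a 95% interval for one-sided 0.025. Print the SD and true difference behind 40 per group. If the level does not match the sizing, restate the power in 5.3 and 13.4.
- **13.4.** Bring its account of the 10 points into line with 5.3.
- **Analysis sets.** Keep intention-to-treat as the deciding analysis and report the same interval against the same margin for the per-protocol set. Requiring both to pass is the sponsor's option. It would cost about 6 to 8 points of power against intention-to-treat alone, and more if the per-protocol set is smaller: with 32 of 45 per arm, joint power at the 90% level is about 69%.
- **Non-normal data.** Use a method tied to the margin, such as a bootstrap interval for the mean difference or a rank-based test or interval shifted by 10, in place of an unshifted rank-sum p-value.

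The cost is wording in 5.3 and 13.1 to 13.4, with no new data. If the level matches the sizing, patient numbers do not change. The downside arises if a 95% interval is chosen but sizing used one-sided 0.05. At SD 18 the power at 40 per group is then 69%, and restoring 80% would take 52 evaluable per arm, or 104 / 0.7 = 149 randomized, above the ceiling of 130.

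### Section 13.1 does not exempt the primary OAB-q outcome from a rank-sum fallback, so a non-normal result would move the non-inferiority comparison off the scale of the 10-point margin

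*Combined protocol and SAP*

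**What the plan says.** Section 5.3 defines the outcome: "The primary outcome for this study is the change in the OAB-q total score from baseline to 3 months". It sets the non-inferiority aim as "showing that the difference between groups is less than 10 points", and says of the planning values: "We used the means and standard deviation for this questionnaire from an unpublished pilot RCT study from Walter Reed". Section 13.4 repeats this: "Power analysis was performed based on previously reported means and standard deviation for the OAB-q".

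Section 13.1 is the only text that assigns tests. Continuous variables get t-tests because normality is expected. Then: "Wilcoxon rank-sum test will be used for continuous variables that are not normally distributed". The change in OAB-q is a continuous variable and has no rule of its own. Sections 13.2 to 13.4 deal with analysis populations and power, and do not override 13.1. No normality criterion is named, and neither test is tied to the margin.

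**The concern.** As written, the observed distribution decides how the primary outcome is compared. The t-test compares means. The rank-sum test, and the Hodges-Lehmann bound that goes with it, concern the median of all TENS-minus-PTNS pairwise differences. The two targets agree when the arms differ only by a shift, and need not agree otherwise.

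The margin and sample size sit on the mean scale. That is an inference: the documents never use the phrase difference in means, but a calculation from means and an SD has no other natural reading.

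Unequal shapes are plausible here. PTNS is given weekly in clinic and TENS is self-administered daily at home, and Section 13.2 keeps non-compliant women in the primary analysis. If a minority of TENS women do much worse than the rest, the data look non-normal and ranks give that minority less weight. In a non-inferiority trial that error favours the new treatment. What is at stake is a non-inferiority claim made when the mean deficit equals the margin.

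**Working it through.** **1. The plan's own figure.** Section 5.3 states "we need 40 patients per group (80 total) to detect no difference with" α = 0.05 and 80% power. The SD is not given, so solve for it from n = 2(z₁₋α + z₀.₈)²SD²/10², which gives SD = 10√(40/2)/(z₁₋α + z₀.₈).
- One-sided 0.05: 44.72/(1.645 + 0.842) = 17.99.
- One-sided 0.025: 44.72/(1.960 + 0.842) = 15.96.

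Sidedness is not stated, so both are carried. The 40 can be neither confirmed nor refuted: SD 15 would need 28 or 36 per arm, and SD 20 would need 50 or 63. For dropout, "Allowing for dropout of up to 30%, we will aim to randomize 114 patients" agrees with 80/0.7 = 114.3, or 57 per arm.

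**2. What the rank comparison targets.** Assume PTNS change is N(25, 12) and TENS is the same, except that a share f is lower by d, with f × d = 10. The true mean deficit is then exactly 10. A TENS-minus-PTNS difference has SD 12√2 = 16.97, and its median m solves (1 − f)Φ(m/16.97) + fΦ((m + d)/16.97) = 0.5.
- f = 0.40, d = 25: 0.6 × 0.287 + 0.4 × 0.819 = 0.50 at m = −9.5.
- f = 0.25, d = 40: 0.75 × 0.342 + 0.25 × 0.974 = 0.50 at m = −6.9.
- f = 0.20, d = 50: 0.8 × 0.376 + 0.2 × 0.996 = 0.50 at m = −5.4.

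The mean deficit is 10 in all three, but the quantity the rank method bounds is 9.5, 6.9 or 5.4. The subgroup's mean change is 25 − d: 0, −15 and −25. Only the first describes women who do not respond; the other two describe women who get worse.

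**3. Error rates.** Simulation with a true mean deficit of 10, 40 per arm and one-sided 5%. The two-stage rule uses the margin-shifted rank test if Shapiro-Wilk gives p < 0.05 in either arm, and the margin-shifted t-test otherwise. The shift, the normality check and the shapes are all assumptions. With 4,000 trials the simulation standard error near 5% is √(0.05 × 0.95/4000) = 0.3 percentage points.

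| Assumed shape | Two-stage | t bound on means |
|---|---|---|
| Normal, pure shift | about 5% | about 5% |
| Both arms equally and strongly skewed | about 5% | about 5% |
| 40% of TENS women do not respond (d = 25) | 6–7% | about 5.5% |
| Non-responders in both arms (PTNS 20–40%, TENS 40 percentage points more) | 4–5% | about 5% |
| One third of TENS women 30 points lower | about 8% | about 6% |
| TENS left-skewed, equal SDs of 17.99 (gamma shape 2 or 1) | 12–15% | about 6% |
| TENS right-skewed, or few large responders | 1–2% | about 4% |
| Stress: 25% of TENS women 40 points lower | 17–19% | 5–6% |
| Stress: 20% of TENS women 50 points lower | about 34% | about 6.5% |

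**4. Sensitivity.** At 57 per arm the left-skewed cases give 13–18% against about 6% for the t bound, so a larger trial does not cure the problem. At one-sided 0.025 with SD 15.96 they give 6.4–8.6% against 3.0–3.5%.

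**The case against.** The t-test is the stated default and the authors expect it to apply, so the switch is a contingency. That is true, but the fallback matters exactly when the expectation fails, and it covers the primary outcome.

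The procedure simulated is not in the protocol. Section 13.1 names no margin-shifted test, confidence bound or normality check. This also stands. The percentages illustrate one reasonable way of carrying out 13.1. The lack of any stated non-inferiority decision rule is a wider gap, to which this point is secondary. Adding a rule that compares a bound with 10 would not settle this point while the switch remains, because in the rank branch the bound would be for another quantity.

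The strongest objection is to size. A reader might infer that ordinary non-response to home TENS would produce false non-inferiority rates of 20–34%. The documents do not support that. With true non-response the normality check fails in only about 13% of trials and the two-stage error is 6–7%. If PTNS also has non-responders, which is as plausible since Section 12.1.1 expects missed sessions there too, there is no inflation. The high figures need a subgroup that deteriorates by 15 to 25 points on average, and nothing in the plan suggests this. They also assume a PTNS SD of 12 against a TENS SD of √(144 + 0.25 × 0.75 × 40²) = 21 or √(144 + 0.20 × 0.80 × 50²) = 23. With a within-group SD of 16–18, the 25%/40-point case falls below 10%.

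**Conclusion.** The defect is real and moderate in size. A written rule lets the data move the primary comparison away from the scale on which the margin and sample size appear to be built, and nothing else in the document prevents it. The effect on error runs from conservative (1–2%), through nominal (4–5%) and slightly raised (6–7%), to two to three times nominal (12–15%) when the TENS arm is left-skewed with equal SDs. Figures of 17–34% are stress cases only. A t-based bound for the mean difference stays at about 4–6.5% over the same shapes, so non-normality at this sample size is no reason to abandon it.

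This rests on reading the margin as a mean difference, on back-solved SDs for the equal-SD cases, and on assumed shapes, normality check and margin shift. It does not show that the trial would reach a wrong conclusion, or that rank-sum misleads whenever data are skewed: if both arms share the same skew it holds its level.

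**What to change.** State in Section 13.1 that the primary non-inferiority comparison is always the difference in mean change in OAB-q total score, with an unequal-variance t-based confidence bound compared with the 10-point margin, whatever the distribution. A bootstrap bound for the same mean difference is an acceptable alternative if skewness is a worry, but choose it in advance. Keep rank-sum as a supportive analysis for this outcome, and say that no normality check selects the primary method. Give the sidedness of α in the same sentence.

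The cost is one sentence and no new data. The downside is a small loss of power if the scores are heavy-tailed with the same shape in both arms.

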PROTOCOL TITLE: INTENSE: INvestigation of TENS Efficacy versus Posterior Tibial Nerve Stimulation for overactive bladder

given a 3-day voiding diary to complete prior to starting their intervention. Urinalysis and urine culture will be obtained to rule out urinary tract infection. This is routinely done on all new patients in our clinic and would be performed on patients not participating in the study as well. Data collected in addition to the above outcome measures includes patient demographics, medical/surgical history, and contact information, which are attached as supporting documents. This information will be collected from the patient on the day of enrollment and we will review the patient's medical record if information is missing or unclear.

The randomization sequence will be generated by computer-based randomization in a sequence that preserves 1:1 randomization and also preserves allocation concealment (likely with randomly alternating block sizes of 6-10 in blocked randomization). Randomization assignments will be completed via REDCAP by a research coordinator. Randomization will only occur after consent has been signed and all baseline data has been obtained.

*12.1. Interventions:*

*12.1.1. PTNS:* Women randomized to the PTNS group will begin therapy after their baseline evaluation is complete. They will be scheduled for PTNS treatment sessions once weekly for 30 minutes, for 12 weeks total. PTNS treatment will be performed as follows:

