40 per group to detect this difference with  $\alpha = 0.05$  and 80% power. To allow for a dropout of up to 30% we will enroll up to 130 patients to account for participants who are lost to follow up. As noted above, we plan to perform both per-protocol and intention-to-treat analysis, and adequate power must be achieved for both per-protocol and intention-to-treat analysis, with the per-protocol patients (those in the PTNS group completing at 12 treatments in a total of 13 weeks) being expected to be a lower sample size and take more recruitment and study follow-up to achieve power.

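### The primary comparison of change in OAB-q is unadjusted, with covariate adjustment left to an undefined trigger; pre-specified adjustment for baseline OAB-q would usually be more precise at almost no cost

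*Combined protocol and SAP*

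**What the plan says.** Section 5.3 defines the endpoint: "The primary outcome for this study is the change in the OAB-q total score from baseline to 3 months". The non-inferiority margin is 10 points, and the stated need is 40 patients per group for 80% power at alpha 0.05.

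Section 13.1 is the only place where the tests are named. It plans "t-tests for continuous variables, as we expect the data will be normally distributed", and otherwise "Wilcoxon rank-sum test will be used for continuous variables that are not normally distributed". Adjustment appears in one conditional sentence: "If there are any baseline differences between groups, a multivariate analysis will determine the contribution of these differences". Sections 13.2 to 13.4 deal with analysis sets and power and mention no covariates.

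Baseline OAB-q is collected in everyone (Section 12: "After enrollment, participants will fill out a baseline OAB-q"; also Table 1) and before allocation: "Randomization will only occur after consent has been signed and all baseline data has been obtained".

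Section 13.4 requires that "adequate power must be achieved for both per-protocol and intention-to-treat analysis", and expects the smaller per-protocol set to need further recruitment and follow-up to get there.

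**The concern.** Two things are unsatisfactory in 13.1.

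First, the adjustment rule cannot be carried out as written. It gives no threshold for a baseline difference, no list of variables and no model. The natural reading is that the unadjusted test is the main comparison and the adjusted result explains it, but the plan does not say what follows for non-inferiority if the two disagree.

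Second, a t-test on change is not a baseline-adjusted analysis. Subtracting baseline fixes its slope at 1. The best-fitting slope is the correlation times the ratio of follow-up SD to baseline SD, and unless that is close to 1 the change score carries avoidable noise.

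The verdict depends on whether a 10-point deficit can be excluded, so the precision of the between-group estimate decides it. The plan's remedy for low power in the per-protocol set is more patients, while baseline adjustment usually gains precision in both sets from data already planned.

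**Working it through.** **Inputs from the documents.** Margin 10 points, 40 per group, 80% power, alpha 0.05 (sidedness not stated), 30% dropout, 114 randomised and up to 130 recruited (Sections 5.2, 5.3, 13.4).

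**Inputs assumed.** The documents print no SD, no baseline-to-follow-up correlation r and no ratio k of follow-up SD to baseline SD. I take r = 0.3, 0.5, 0.7 and k = 0.8, 1.0, 1.2, a true difference of 0, and both one-sided 0.05 and one-sided 0.025.

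**The plan's own figures.** The 40 per group cannot be reproduced without an SD, so I solve backwards (noncentral t, 78 df). An SD of change of 17.83 at one-sided 0.05, or 15.77 at one-sided 0.025, gives exactly 80%. The dropout step agrees to within rounding: 80/0.7 = 114.3, against 114 stated. The 40 per arm is therefore the full-dropout case (114 × 0.7 = 79.8).

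**Variance.** In units of the baseline variance, the variance of change is 1 + k² − 2rk, and the baseline-adjusted variance is k²(1 − r²). With k = 1 the ratio is (1 − r²)/(2 − 2r) = (1 + r)/2.

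| k | variance cut, r = 0.3 | r = 0.5 | r = 0.7 |
|---|---|---|---|
| 1.0 | 35.0% | 25.0% | 15.0% |
| 1.2 | 23.8% | 12.9% | 3.4% |
| 0.8 | 49.8% | 42.9% | 37.2% |

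**Power.** The adjusted model uses 2n − 3 df and a variance inflation of 1 + 1/(2n − 4) for estimating the slope. Ranges span the two alpha levels.

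| n per arm | k | unadjusted t-test | adjusted, r = 0.3 | r = 0.5 | r = 0.7 |
|---|---|---|---|---|---|
| 40 | 1.0 | 80% | 92-93% | 89-90% | 85-86% |
| 50 | 1.0 | 87-88% | 96-97% | 94-95% | 91-92% |
| 57 | 1.0 | 91-92% | 98-99% | 96-97% | 94-95% |
| 40 | 1.2 | 80% | 88-89% | 84-85% | 81% |
| 40 | 0.8 | 80% | 97-98% | 95-96% | 93-94% |

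The 57 per arm is 114 with no dropout. At r = 0.5 and k = 1 the gain is about 9, 7 and 5 points at 40, 50 and 57 per arm. In the worst case, a true slope of exactly 1, power at 40 per arm is 79.5%, a loss of half a point.

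**How often the two analyses disagree.** In simulation (40 per arm, k = 1, true difference 0) the t-test and the adjusted model reach opposite non-inferiority verdicts in about 15%, 12% and 9% of trials for r = 0.3, 0.5 and 0.7.

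**What the conditional rule might recover.** The plan defines no trigger, so this is illustrative only. Suppose the adjusted model replaces the t-test when a baseline OAB-q comparison falls below a p-value cut-off (200,000 trials per cell, 40 per arm, k = 1, r = 0.5). Power is 81% at p<0.05, 83% at p<0.20 and 85-86% at p<0.50, against 89% when adjustment is always used at one-sided 0.05 (89.5% at 0.025). Across r = 0.3 to 0.7 these cut-offs recover about 9-11%, 30-35% and 60-66% of the gain. Type I error was not inflated: 0.036-0.047 against 0.05, and 0.017-0.023 against 0.025.

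**The case against.** The strongest reply is that this is a matter of efficiency and not an error. The unadjusted test is unbiased under randomisation, and a trigger fixed in advance did not raise the false non-inferiority rate. That stands, and it limits the weight of the point.

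Four further objections bear on its size:

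- **Disagreement is mostly the power gain seen again.** At r = 0.5 and one-sided 0.05, of the 12.2% of discordant trials, 10.4 points are successes only for the adjusted model and 1.8 points go the other way. At 57 per arm total disagreement falls to roughly 5-8%. This is correct, so the disagreement figure should not be added to the power gain as a second harm.
- **The trigger simulation is not the plan's rule.** The natural reading keeps the unadjusted test as the main comparison. Correct. On that reading the main comparison recovers none of the gain.
- **The pilot SD may be a raw-score SD.** Section 5.3 does not say which it is. On that reading (40 per arm, k = 1, one-sided 0.05) power goes from 68% to 83%, 80% to 89% and 94% to 96-97% for r = 0.3, 0.5 and 0.7, so the gain is about 15, 9 or 2 points. The size changes but the direction does not.
- **Recruitment may reach 130.** At 65 per arm without dropout the t-test already has 94-95% power, and the gain at r = 0.5 is about 4 points. This is true for a complete intention-to-treat set, but the per-protocol set is expected to be smaller.

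**Conclusion.** The point holds as a recommended improvement. Section 13.1 leaves the primary comparison unadjusted and makes adjustment depend on a condition it does not define, although a valid baseline covariate is available for every participant. With the back-solved change-score SD, equal variances and r between 0.3 and 0.7, pre-specified adjustment is worth about 5 to 13 points of power at 40 per arm. That falls to under 1 point at k = 1.2 and r = 0.7, and the worst case is a loss of half a point. Confidence is high in the direction and the recommendation. The individual figures are illustrations, because r, the SDs and the sidedness are not in the documents. The planned test is not invalid, and nothing here argues for a smaller sample.

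**What to change.** In Section 13.1, define the primary analysis as the TENS minus PTNS difference from a linear model of the 12-week OAB-q total score on treatment and baseline OAB-q. Modelling change with the same covariate gives the same treatment estimate. Compare that model's confidence interval with the 10-point margin, in both the intention-to-treat and per-protocol sets.

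Delete the sentence that makes adjustment depend on observed baseline differences. State that the Wilcoxon test does not replace this model for the primary outcome, since as specified it is a test and supplies no interval to set against the margin. Keep the unadjusted comparison of change as a sensitivity analysis.

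The cost is a few sentences and one degree of freedom, with no new data or visits.
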